10.6 Immune-related Adverse Events

All treatment-emergent adverse events will be analyzed to identify those that potentially are immunerelated. To identify all possible cases, a broad-scope search on Standardized MedDRA Queries (SMQs), including 'Hypersensitivity', 'Anaphylactic reactions', 'Angioedema' and 'Severe cutaneous adverse reactions' will be considered. Moreover, to identify the potential cases manifested by nonspecific symptoms and not covered by these SMQs, other MedDRA PTs like 'Musculoskeletal pain', 'Asthenia', 'Pyrexia', 'Chills', 'Body temperature increased', 'Influenza like illness', 'Injection related reaction', 'Presyncope' and 'Syncope' will also be taken into account. Hypersensitivity reactions manifested by local symptoms will be identified using the MedDRA high level term (HLT) 'injection site reactions'. The SMQs may include very specific as well as less specific terms; hence a narrowscope search on these SMQs will be carried out to identify those cases that are highly likely to represent an immune-related etiology.

Potential immune-related adverse events will be tabulated using the SMQs and PTs, for the fresh cycle, cumulatively for the cryopreserved cycles (overall and by programmed and natural cycles separately), and for the trial across the fresh and cryopreserved cycles.

10.7 Cycle Cancellations due to an Adverse Event, including Immune-related Adverse Events, or due to Technical Malfunctions of the Administration Pen

A summary table will be prepared showing the proportion of subjects with cycle cancellations including reason for cancellation for the fresh cycle. If the cycle is cancelled due to an adverse event, it will be further categorized as immune-related or not.

Any cancellations in the cryopreserved cycles due to the COVID-19 pandemic will also be summarized.

10.8 Ovarian Hyperstimulation Syndrome (OHSS),

OHSS will for each treatment group be tabulated by classification (mild, moderate, severe) and grade (1, 2, 3, 4, 5). The tabulation will also include the total incidence of OHSS and the incidence of moderate/severe OHSS. OHSS will be presented overall and by timing (early, late, and early and late combined).

For the fresh cycle, early OHSS is defined as OHSS with onset ≤ 9 days after triggering of final follicular maturation. Note this includes OHSS with onset before triggering and OHSS with onset during stimulation where triggering is not performed. Late OHSS is defined as OHSS with onset >9 days after triggering of final follicular maturation.

Early and late OHSS will be also tabulated by classification (mild, moderate, severe) and grade (1, 2, 3, 4, 5).

Ferring Pharmaceuticals

Separate tabulations will be made for the fresh cycle, cumulatively for the cryopreserved cycles (overall and by programmed and natural cycles separately), and for the trial across the fresh and cryopreserved cycles.

10.9 Hospitalization and Paracentesis due to Ovarian Hyperstimulation Syndrome

The number and percentage of subjects hospitalized due to OHSS as well as the number and percentage of subjects who underwent paracentesis due to OHSS will be tabulated. Separate tabulations will be made for the fresh cycle, cumulatively for the cryopreserved cycles (overall and by programmed and natural cycles separately), and for the trial across the fresh and cryopreserved cycles.

10.10 Multi-fetal Gestation, Biochemical Pregnancy, Spontaneous Abortion, Ectopic Pregnancy and Vanishing Twins

Summary tables will be prepared for these endpoints. Separate tabulations will be made for the fresh cycle, cumulatively for the cryopreserved cycles (overall and by programmed and natural cycles separately), and for the trial across the fresh and cryopreserved cycles.

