pregnancies / births and the related neonatal health problems. To minimize the incidence of multiple gestations, a restrictive transfer policy guided by blastocyst quality and limited to no more than double blastocyst transfer in both the fresh and the cryopreserved cycles is mandatory in this trial. The incidence of miscarriage and ectopic pregnancy is higher in women undergoing controlled ovarian stimulation than in women conceiving spontaneously, though the risk of ectopic pregnancy is mainly higher in women with a history of tubal infertility. Furthermore, the prevalence of congenital malformations after ART may be slightly higher than after spontaneous conceptions; this is thought to be due to differences in parental characteristics (e.g. maternal age, maternal and paternal genetic background, and sperm characteristics) and multiple pregnancies.

Benefits / Risks

Participation in this trial does not create extra risks for the subjects compared to routine controlled ovarian stimulation. The majority of subjects will receive active treatment, with an expected likelihood of conceiving similar to that in standard clinical practice. Subjects who exhibit poor response to therapy as per pre-established protocol criteria will be offered medication and financial support for an ART cycle with an approved gonadotropin preparation outside of the trial. In conclusion, the evaluation of benefits and risks indicate that participation in this trial is associated with a favorable benefit-risk ratio.

Date: 25 Apr 2018 E-Study Protocol-22377; Ver. 1.0 Supersedes: None Page 33 of 159

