- Number of cryopreserved cycles initiated within 12 months from the start of controlled ovarian stimulation, and number and percentage of cryopreserved cycles with blastocyst transfer

- Circulating concentrations of AMH, FSH, LH, estradiol, progesterone, inhibin A and inhibin B on stimulation day 5, end-of-stimulation and oocyte retrieval, and FSH population pharmacokinetic parameters
- Total gonadotropin dose, number of stimulation days and number of dose adjustments
- Frequency and intensity of adverse events
- Changes in circulating levels of clinical chemistry and haematology parameters and proportion of subjects with markedly abnormal changes
- Frequency and intensity of injection site reactions (redness, pain, itching, swelling and bruising) assessed by the subject during the stimulation period
- Proportion of subjects with treatment-induced anti-FSH antibodies, overall as well as with neutralizing capacity
- Frequency and intensity of immune-related adverse events
- Proportion of subjects with cycle cancellations due to an adverse event, including immunerelated adverse events, or due to technical malfunctions of the administration pen
- Proportion of subjects with OHSS, overall and by grade, and proportion of subjects with moderate/severe OHSS
- Proportion of subjects hospitalized due to OHSS and proportion of subjects undergoing paracentesis due to OHSS
- Rate of multi-fetal gestation, biochemical pregnancy, spontaneous abortion, ectopic pregnancy (with and without medical/surgical intervention) and vanishing twins in the fresh cycle and in the cryopreserved cycles
- Technical malfunctions of the administration pen

Post-trial Endpoints

- Cumulative live birth rate after the fresh cycle and cryopreserved cycles initiated within 12 months from the start of controlled ovarian stimulation
- Live birth rate in the fresh cycle and in the cryopreserved cycles
- Live birth rate of singletons born at term (≥37 weeks of gestation) in the fresh cycle, the cryopreserved cycles and cumulatively
- Time from start of controlled ovarian stimulation to live birth of a singleton born at term across the fresh and cryopreserved cycles, including duration and number of cycles before achieving a live birth of a singleton born at term
- Rate of minor/major congenital anomalies at birth, 4 weeks and 1 year after birth in the fresh cycle and cryopreserved cycles

3 Trial Design and Sample Size Considerations

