9.4.1 Ongoing Pregnancy Rate

The ongoing pregnancy rate will be calculated and tabulated for the fresh cycle and for each cryopreserved cycle sequentially (overall and within programmed and natural cryopreserved cycles separately), and for cryopreserved cycles cumulatively based on both the total number of subjects in the treatment group and the total number of subjects who started the respective cycle.

Note that, as a result of late pregnancy loss (after confirmation of ongoing pregnancy), a subject is allowed to come back for another transfer within one year from the start of stimulation, as long as there is at least one blastocyst remaining. The eCRF will be kept open for the subject to capture potentially further cryopreserved cycle information up to one year from the start of stimulation unless the subject withdraws consent or when all her blastocysts are exhausted. Therefore, a subject may achieve more than one ongoing pregnancy within two different cycles in the trial, but for cumulative ongoing pregnancy rates, a subject can only be counted once in the numerator.

Analyses similar to that used for the primary endpoint will be applied for the fresh cycle, and for cryopreserved cycles as applicable i.e. where there is at least one subject who started the respective cycle in both treatment groups and will be applied to both the mITT and PP analysis sets.

For subjects with an ongoing pregnancy, the number of intrauterine viable fetuses will be tabulated overall and by ongoing pregnancy in sequential order.

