9.4.4 Clinical Pregnancy Rate

The clinical pregnancy rate will be calculated for the fresh cycle, for each cryopreserved cycle sequentially (overall and within programmed and natural cycles separately), cumulatively for the cryopreserved cycles, and cumulatively across the fresh and cryopreserved cycles based on both the total number of subjects in the treatment group and the total number of subjects who started the respective cycle. The analyses will be conducted in a similar manner as ongoing pregnancy rate and will be applied to both the mITT and PP analysis sets. For subjects with clinical pregnancy, the type of clinical pregnancy (intrauterine or ectopic) will be tabulated.

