10.1 General Considerations

Analyses for the safety analysis set will be conducted according to the actual treatment received.

Data will be presented by summary tables and listings. Categorical data will be summarized by treatment using the number and percentage of subjects in each category. For calculation of percentages, the denominator will be the total number of subjects in the respective treatment group in the safety analysis set. Continuous data will be summarized by treatment using number, mean, standard deviation, median, minimum, and maximum.

All individual subject data will be listed per subject and treatment as observed including any derived values.

Missing Data

Missing values will be treated as missing, except for causality, intensity, seriousness, and outcome of adverse events. A worst-case approach will be used: if causality is missing, the adverse event will be regarded as related to the IMP; if the intensity of an adverse event is missing, the adverse event will be regarded as severe; if seriousness is missing, the adverse event will be regarded as serious; if outcome is missing, and no date of outcome is present, the outcome is regarded as 'ongoing'.

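### SAP 10.10 sets no pregnancy-based denominator, so biochemical pregnancy, spontaneous abortion and vanishing twin rates default to all treated women, most of whom were never at risk

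*SAP*

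**What the plan says.** The endpoint list in SAP 2.2 defines the endpoint as "Rate of multi-fetal gestation, biochemical pregnancy, spontaneous abortion, ectopic pregnancy (with and without medical/surgical intervention) and vanishing twins in the fresh cycle". Frozen cycles are covered too. The list does not say what the rate is a rate of.

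SAP 10.10 gives the analysis: "Summary tables will be prepared for these endpoints. Separate tabulations will be made for the fresh cycle", then for the cryopreserved cycles and for the trial as a whole. No denominator is named. Protocol 9.8.2.9 is equally silent.

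The general safety rule in SAP 10.1, repeated in Protocol 9.8.1, reads: "For calculation of percentages, the denominator will be the total number of subjects in the respective treatment group in the safety analysis set". SAP 10.10 makes no exception to it.

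Two displays in the efficacy part are conditional on pregnancy:

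- SAP 9.4.1: "For subjects with an ongoing pregnancy, the number of intrauterine viable fetuses will be tabulated overall and by ongoing pregnancy in sequential order".
- SAP 9.4.4: "For subjects with clinical pregnancy, the type of clinical pregnancy (intrauterine or ectopic) will be tabulated".

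Protocol 7.2.9 and 8.3.2 define all five events in terms of a positive beta-hCG test, gestational sacs or fetuses. Protocol 8.3.2 also has pregnancy losses reported as adverse events, so they enter the per-subject adverse event tables as well. Multi-fetal gestations do not (Protocol 8.4.4).

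**The concern.** A woman who does not conceive cannot miscarry or lose a twin. A percentage over all treated women is therefore the product of two quantities: the chance of becoming pregnant and the risk once pregnant. The second is what a clinician needs when counselling a pregnant patient, and it is what bears on the stated safety rationale of the design: "To minimize the incidence of multiple gestations, a restrictive transfer policy guided by blastocyst quality" is mandated in both the fresh and the cryopreserved cycles (Protocol 1.3).

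Two things are at stake. Within the FE 999049 arm, loss rates per treated woman are lower than the risk a pregnancy carries. Across arms, the table will show many more losses on FE 999049 simply because that arm has many more pregnancies, and a reader may take this for a higher risk of loss.

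**Working it through.** **Inputs from the documents (SAP 3.2, same in Protocol 9.1).** Cumulative ongoing pregnancy rate on FE 999049: about 30%. Placebo pregnancy rate: not above 3%. Sample size: 500 and 50. The documents give no rate for a positive beta-hCG, multi-fetal gestation or pregnancy loss, so there is no stated figure for these endpoints to reproduce. The power of at least 99% built on 30% against 3% does reproduce: 0.99999 by the normal approximation (two-sided 0.05) and 0.9999 by one-sided Fisher at 0.025. The inputs are thus read as the plan uses them.

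**Formula.** With at most one pregnancy counted per woman, rate per treated woman = share pregnant × risk per pregnancy. The factor by which the per-woman rate understates the per-pregnancy risk is 1/(share pregnant).

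**Understatement within an arm.**

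- FE 999049, documents' 30%: 1/0.30 = 3.3.
- FE 999049, assumed share with any pregnancy of 35%, 40%, 45%, 50%: 1/0.35 = 2.9, 1/0.40 = 2.5, 1/0.45 = 2.2, 1/0.50 = 2.0.
- Placebo, documents' 3%: 1/0.03 = 33.

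**Contrast between arms at equal loss risk per pregnancy.** Assume a loss risk of 20% in both arms (range 10-30%).

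- FE 999049: 0.30 × 0.20 = 6.0%, or 30 of 500 women (range 3.0-9.0%).
- Placebo: 0.03 × 0.20 = 0.6%, or 0.3 of 50 women (range 0.3-0.9%).
- Ratio: 0.30/0.03 = 10 for any common loss risk, since that risk cancels.

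The 30% counts ongoing pregnancies, whereas early losses come from a larger pool. If both arms are scaled up by 1/(1 − 0.20), the shares are 37.5% and 3.75%, the per-woman rates 7.5% and 0.75%, and the ratio is still 10.

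**Multi-fetal gestation.** An assumed 5% of ongoing pregnancies (range 3-10%) appears as 0.30 × 0.05 = 1.5% of treated women (range 0.9-3.0%). For this endpoint SAP 9.4.1 already shows the conditional figure.

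**Which events lack a pregnancy-based display.**

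- Multi-fetal gestation at 8-9 weeks: covered by SAP 9.4.1.
- Ectopic pregnancy: covered by SAP 9.4.4.
- Biochemical pregnancy and spontaneous abortion: none specified.
- Vanishing twin: none specified. The fetus count at 8-9 weeks cannot supply it, because a twin pregnancy already reduced to one fetus is counted as a singleton.

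**Placebo pregnancies expected.** 0.03 × 50 = 1.5.

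**The case against.** SAP 10.10 does not itself say per treated woman. SAP 2.2 uses a proportion of subjects for OHSS and antibodies but a rate for these events, which leaves room for another denominator, and the table shells are in a separate document that may settle it. This stands in part: the per-woman denominator is a default inferred from SAP 10.1. But where the SAP wants a different denominator it says so, as with cycle starters in 9.4.1 and 9.4.4, and shells should follow the SAP text.

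A reader might infer that the multiple-gestation result is hidden. The documents do not support that, because SAP 9.4.1 gives fetus number among ongoing pregnancies. The same holds for ectopic pregnancy through SAP 9.4.4.

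A reader might also call the excess on FE 999049 false, or say the plan makes the drug appear to cause losses. That goes too far. Per treated woman is the comparison that randomization protects, and if treatment produces pregnancies, treated women do have more losses. A per-pregnancy contrast conditions on a post-randomization outcome. SAP 10.10 plans descriptive tables and no test.

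Finally, pregnancy rates at each stage are tabulated by arm and cycle, so a reader could try to derive loss fractions. That substitute is imperfect. SAP 9.2.2 imputes missing pregnancy outcomes as negative, so a woman lost to follow-up looks like a loss. In cumulative ongoing pregnancy rates a woman counts once (SAP 9.4.1), so a loss followed by an ongoing pregnancy disappears. The two errors run in opposite directions.

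**Conclusion.** The concern holds as a matter of display. Followed as written, SAP 10.1 and 10.10 put biochemical pregnancy, spontaneous abortion and vanishing twins over a group mostly not at risk, and no other table gives these three per pregnancy.

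The 3.3-fold understatement and the 10-fold descriptive contrast rest on the documents' 30% and 3%. The contrast also assumes equal risk per pregnancy. The 2.0- to 2.9-fold range rests on an assumed 35-50% of women with any pregnancy. A reader might reach 13- to 17-fold by assuming 40-50% beta-hCG positive on FE 999049 while leaving placebo at 3% (0.40/0.03 and 0.50/0.03). That raises the share in one arm only, and the documents do not support it.

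The documents support a risk of misreading the 10-fold contrast, not a planned wrong conclusion. No primary, key secondary or tested result changes.

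**What to change.** In SAP 10.10, keep the percentage per treated woman as the randomized comparison and add beside it a descriptive per-pregnancy percentage:

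- biochemical pregnancy and spontaneous abortion over pregnancies with a positive beta-hCG, with spontaneous abortion also over clinical pregnancies;
- ectopic pregnancy over clinical pregnancies, with a cross-reference to SAP 9.4.4;
- multi-fetal gestation and vanishing twins over vital and over ongoing pregnancies, with a cross-reference to SAP 9.4.1.

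Add a note that the placebo per-pregnancy figures will rest on very few pregnancies, about 1.5 expected, and should not be compared between arms.

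The counts are already collected. The cost is a few lines of SAP text and one extra column per table. The downside for the sponsor is that the displayed rates become less favourable.

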10.11 Pen Malfunction

The frequency of reported malfunctions of the administration pen will be presented in a summary table. For confirmed pen malfunctions, the categories include: not able to detach the pen cap, not able to click / screw-on the needle due to damaged thread on cartridge holder, not able to dial the dose, not able to inject the dose, and other.

10.12 Physical Examination

Physical examination at end-of-cycle in the fresh cycle compared to screening will be summarized in shift tables and all subjects with any abnormal finding will be listed per subject. For each cryopreserved cycle, physical examination at end-of-cycle in the cryopreserved cycle compared to cycle initiation in the respective cycle will be summarized in shift tables and all subjects with any abnormal finding will be listed per subject.

10.13 Gynecological Examination

Gynecological examination at end-of-cycle in the fresh cycle compared to screening will be summarized in shift tables and all subjects with any abnormal finding will be listed per subject. For each cryopreserved cycle, gynecological examination at end-of-cycle in the cryopreserved cycle compared to cycle initiation in the respective cycle will be summarized in shift tables and all subjects with any abnormal finding will be listed per subject.

10.14 Vital Signs

Vital signs (systolic and diastolic blood pressure and pulse) will be measured at screening, on stimulation day 1 prior to the first exposure to IMP and at end-of-cycle in the fresh cycle as well as at cycle initiation and at end-of-cycle in any cryopreserved cycle.

In the fresh cycle, the baseline for the vital sign analyses will be the values obtained at the last assessment prior to the first exposure to IMP.

10.14.1 Summary Statistics

Mean change and mean percentage (%) change from baseline at each time point will be presented for each vital sign variable by cycle in a sequential order (overall and within programmed and natural cycles separately). In addition, descriptive statistics, i.e., the number of subjects with data, mean (standard deviation), median, minimum, and maximum values, will be presented for observed values and change from baseline at each time point by cycle sequentially (overall and within programmed and natural cycles separately) for each vital sign variable.

10.14.2 Changes Relative to Normal Range

Shift tables will be prepared to compare baseline values to the end-of-cycle values, using a categorization of low, normal and high values at each visit by cycle sequentially (overall and within programmed and natural cycles separately). Low, normal and high are defined in Appendix 1.

10.14.3 Markedly Abnormal Changes

Summary tables will be prepared displaying the proportion of subjects who have at least one markedly abnormal value in the fresh cycle, cumulatively for the cryopreserved cycles (overall and by programmed and natural cycles separately), and for the trial across the fresh and cryopreserved cycles.. The table will also include a break-down by classification of the baseline value. Markedly abnormal criteria for vital signs are specified in Appendix 1.

10.14.4 Data Listings

Data listings will be prepared by treatment group, subject number for all subjects with any abnormal vital sign value at any time point.

11 **Post-trial Assessments**

11.1 Post-trial Efficacy Assessments

11.1.1 Cumulative Live Birth Rate

The live birth rate will be calculated cumulatively across the fresh and cryopreserved cycles. Subjects with no information on live birth will be defaulted to a negative response.

The cumulative live birth rate is regarded as a key secondary endpoint and will be formally tested for treatment efficacy between the FE999049 treatment group and the placebo group using a hierarchical procedure. Upon achieving statistical significance about the primary endpoint at the 0.05 alpha level, the cumulative live birth rate will be tested at the 0.05 alpha level for inferential conclusions, using a similar method to the primary efficacy analysis.

Similarly to the primary efficacy endpoint, sensitivity analysis will be conducted for the subjects in the PP analysis set as sensitivity analysis, as well as in the ITT analysis set if the ITT analysis set differs from the mITT analysis set. Furthermore, the additional sensitivity analyses due to the COVID-19 pandemic will be repeated. Descriptive statistics will be presented by treatment group.

11.1.2 Live Birth Rate

The live birth rate will be calculated for the fresh cycle, for each cryopreserved cycle sequentially (overall and within programmed and natural cycles separately), cumulatively for the cryopreserved cycles, and cumulatively across the fresh and cryopreserved cycles based on both the total number of subjects in the treatment group and the total number of subjects who started the respective cycle. Subjects with no information on live birth will be defaulted to a negative response. Descriptive statistics will be presented by treatment group.

